## 9.2 Subgroups by Antibody Serostatus, Plasma Antigen, and Viral RNA Levels

An addendum to the SAP for version 1 of TICO, dated 14 April 2021, described analysis plans for antibody, antigen, viral RNA levels and biomarkers of inflammation and coagulation for monoclonal antibodies studied in TICO. This analysis plan was developed before the corresponding biomarker data were available. Results for the first three investigational agents, bamlanivimab, sotrovimab, and BRII-196/198, were published. These analyses informed the current analysis plan for antibody, antigen, and viral RNA data.

This section motivates and describes subgroup analyses by baseline antibody serostatus, plasma antigen levels, and viral RNA levels. Assays are described in [Appendix F](#). Briefly, plasma samples collected at study entry and at days 1, 3 and 5 were used to measure anti-spike receptor binding domain (RBD) neutralizing antibodies (nAbs) in a surrogate viral neutralization test, anti-nucleocapsid (anti-N) binding antibody levels, and semi-quantitative anti-Spike IgG levels. Qualitative and quantitative plasma SARS-CoV-2 N antigen was measured using a microbead-based immunoassay by Quanterix (Billerica, MA, USA). SARS-CoV-2 viral RNA levels were measured from a mid-turbinate nasal swab. SARS-CoV-2 genome sequencing and variant identification were also determined using Illumina whole genome sequencing of the mid-turbinate nasal swab at baseline.

Statistical models for the subgroup analyses depend on the investigated endpoint, and were described in section [9.1](#).

The two key subgroup hypotheses concern a differential treatment effect (active versus placebo) across subgroups by nAb serostatus for nMAb and antiviral treatments:

**Hypothesis 1:** Patients who are nAb seronegative (GenScript ELISA) at study entry will benefit more from the investigational agent (compared to placebo) than patients with higher endogenous antibody levels. Furthermore, those who are nAb seronegative AND have high antigen levels will benefit more from the investigational agent compared to placebo than other subgroups categorized by both antibody and antigen levels.

**Hypothesis 2:** Patients who are nAb seronegative (Genscript) AND have high levels of RNA from nasal turbinate swab will benefit more from the investigational agent compared to placebo than other subgroups categorized by both antibody and RNA levels.

To address these hypotheses, the following subgroups will be considered:

- Participants who are **nAb** negative at study entry, versus nAb positive. SARS-CoV-2 anti-spike neutralizing antibody levels by GenScript are expressed as percent binding inhibition. Specimens with levels < 30% are considered nAb negative (30% is the manufacturer's cutoff for positivity), specimens with levels  $\geq$ 30% are considered nAb positive. In the TICO bamlanivimab trial, 50% of participants had endogenous nAbs (i.e., were nAb positive).
- Subgroups by **plasma antigen** level will be formed by using the median antigen level at study entry as a cut-point (< median versus  $\geq$  median). In the TICO bamlanivimab trial, the median antigen level was approximately 1000 ng/L.
- Four subgroups formed by the bivariate combinations of nAb status (negative versus positive) and plasma antigen levels (< median versus  $\geq$  median).
- Subgroups by **Viral RNA** levels by qualitative RT-PCR analysis on mid-turbinate nasal swabs will be formed using the median RNA levels (< median vs  $\geq$  median). In the TICO bamlanivimab trial, the median was approximately 10,000 cp/mL.
- Four subgroups formed by the bivariate combinations of nAb status (negative versus positive) and viral RNA levels (< median versus  $\geq$  median).

Subgroup analyses will be performed for the **efficacy and safety outcomes** listed in section 9.1. The key efficacy outcome for the subgroup analyses will be time to *sustained recovery* through day 90, and key safety outcomes will be the composite of death, SAEs, organ failure and serious infections through day 90, mortality through day 90, and the composite of death, SAEs, organ failure, serious infections, and grade 3 or 4 AEs through day 28. Methods are described in section 9.1 above.

**Comment:** In TICO, the neutralizing antibody status is determined at a central lab; while the baseline antibody status is being determined on an ongoing basis while the trial is enrolling, there is some delay due to batch shipping and processing time. Subgroup analyses by baseline nAb status will be included in interim reports to the DSMB when sufficient data are available for meaningful analyses.

Similar hypotheses as for the nAb subgroups will be assessed for subgroups formed by the additional two antibody assays; these analyses will be considered exploratory:

- Subgroups formed by **anti-N antibody status** (positive versus negative at study entry), and bivariate subgroups formed by the combinations of anti-N Ab status and plasma antigen or viral RNA levels. Anti-N antibody levels are measured using a SARS-CoV-2

antibody assay by **BioRad** (Hercules, CA, USA) measuring total (IgA, IgG, and IgM) anti-nucleoprotein. For the subgroup analyses, participants with anti-N levels  $<1$  will be considered “anti-N Ab negative”, those with levels  $\geq 1$  will be considered “anti-N Ab positive”.

**Comment:** Results of the BioRad anti-N antibody measurement are defined in terms of “specimen ratios”. According to the manufacturer, specimen ratios less than 0.8 are considered negative, those with a specimen ratio between 0.8 and 1.0 are considered equivocal, and those  $\geq 1.0$  are considered positive for the presence of anti-SARS-CoV-2 antibodies. For the subgroup analyses, participants with negative and equivocal anti-N Ab results will be combined and referred to as “anti-N negative”.

- Subgroups formed by **quantitative anti-Spike IgG** (Quanterix) antibody status (positive versus negative), and bivariate subgroups formed by the combinations of anti-Spike IgG status and plasma antigen or viral RNA levels. Specimens with antibody levels  $< 770$  ng/mL will be considered “anti-Spike IgG antibody negative”, those with levels  $\geq 770$  ng/mL will be considered “anti-Spike IgG positive”.

### **Motivation for the hypotheses:**

In the TICO bamlanivimab trial, there was no difference in time to sustained recovery by day 90, RRR=0.99 (95% CI: 0.79 to 1.22),  $p=0.89$ . However, the treatment effect varied by nAb status at baseline; among patients who were nAbs negative and positive at entry, the RRRs were 1.24 (95% CI: 0.90-1.70) and 0.74 (95% CI: 0.54-1.00), respectively ( $p=0.02$  for differential treatment effect). This means, there was a trend towards benefit with bamlanivimab among those who did not have endogenous nAbs at study entry, while time to sustained recovery was longer with bamlanivimab compared to placebo among those who already had endogenous nAbs. Moreover, among those who were nAb negative, the difference between bamlanivimab and placebo was more evident if plasma antigen or nasal-swab viral RNA were above the median levels at study entry. Results for subgroups by anti-N Ab status had a similar pattern, but less pronounced.

### **Motivation for safety analyses by nAb status:**

In an analysis of the combined data for first three nMAbs investigated in TICO (bamlanivimab, sotrovimab, and BRII-196/198), the risk of the composite safety outcome of *death, SAE, organ failure, or serious infections through Day 90* was similar in the “active” versus placebo arms, but a safety signal was identified among participants with pre-existing endogenous neutralizing antibodies (nAbs). Specifically, the risk of the composite outcome at day 90 was 25.3% in the (pooled) active arms compared with 27.2% in the (pooled) placebo groups, HR=0.95 (95% CI: 0.72 to 1.25). The treatment effect on the composite safety outcome at day 90 differed by nAb serostatus at baseline, however; in participants who were nAb negative at baseline, HR=0.72 (95% CI: 0.50 to 1.02) (HR<1 favors the “active” group), and HR=1.42 (95% CI: 0.91 to 2.22) (favoring the placebo group) among those who were nAb positive at baseline, nominal  $p$ -value for interaction  $p=0.02$ . In the placebo group, the rate for the composite safety endpoint was higher among those who were nAb negative at baseline compared with those who were nAb positive (33% versus 20%, respectively); those who were nAb negative at baseline were sicker from COVID-19 at study entry and also had a lower chance of *sustained recovery*. Mortality followed a similar pattern as the composite outcome; there was no evidence for a difference between the active versus placebo groups in the overall analyses (pooled across the three nMAbs), HR=1.13 (95% CI: 0.67 to 1.88), while the treatment effect on mortality differed

according to baseline nAb status, with HR=0.72 (95% CI: 0.39-1.33) (HR<1 favoring the active arm) among those who were nAb negative, compared to HR=3.64 (95% CI: 1.05 to 12.65) among those who were nAb positive.

## 10 Interim Monitoring Guidelines for the DSMB

Each investigational agent versus placebo comparison will be treated as a separate clinical trial; stopping boundaries will be derived to allow for multiple interim looks, but will not be additionally inflated to adjust for simultaneous analysis of multiple investigational agents, except when explicitly stated in the agent-specific protocol appendix and statistical analysis plan.

The DSMB will be asked to recommend early termination or modification only when there is clear and substantial evidence of a treatment difference (unless a trial is stopped for futility).

### 10.1 Early Assessment of Safety

For investigational agents with minimal pre-existing data, the pace of enrollment will be initially restricted and the DSMB will be asked to review safety data for the first 20 to 30 participants before increasing the pace of enrollment.

Subsequently, the DSMB will carry out regular reviews of safety data reports. These reports will include summaries of infusion-related events, grade 1-4 AEs, SAEs, organ failure, serious infections, and deaths, including the primary safety outcome at Day 5, and Day 28. Event listings for incident grade 3 and 4 AEs, SAEs, organ failure and serious infections, SUSARs, UPs and deaths will be provided (events that were reported since the previous review will be marked). Narratives will be provided for selected SAEs, SUSARs or UPs, particularly those judged related to study treatment. Analyses are described in section 7.

#### Monitoring boundary for harm:

- Until the first 300 participants are enrolled (150 per study arm) and the early futility analysis is conducted, the treatment groups will also be compared for the “pulmonary” and “pulmonary+” ordinal outcomes at Day 5, using a proportional odds model stratified by study pharmacy and pulmonary+ outcome category at baseline. A Haybittle-Peto boundary with 2.5 standard deviation (SD) for the first 50 participants enrolled and 2.0 SD afterwards will be used as a guideline for harm.
- After the study population is expanded to include disease severity stratum 2, these analyses are performed by disease severity stratum.

At the discretion of the DSMB, these safety reports will be prepared at a frequency they specify, for example, weekly. The DSMB may also request additional data summaries.

## 10.2 Early Assessment of Futility

### 10.2.1 Interim Monitoring Guidelines for Early Assessment of Futility

Early in the trial, enrolment is restricted to participants in disease severity stratum 1. When Day 5 data for the first (approximately) 300 participants (150 per study arm) are available, the DSMB will review interim data and use pre-specified guidelines for early evidence of sufficient activity of the investigational agent that justifies continuing enrolment for the agent and expanding eligibility criteria to include participants in disease severity stratum 2 as well as stratum 1. Because the risk-benefit trade-off may be more complex than can be captured in pre-specified guidelines, decisions to terminate an agent for futility will include a broad assessment of the available data, and may be postponed until more data is available.

The early futility monitoring uses two co-primary outcomes, denoted by “pulmonary” and “pulmonary+”, assessed on Day 5. Both are ordered categorical outcomes with 7 categories, described in section 4.1 of the protocol and in [Appendix A](#) to this SAP. The pulmonary outcome considers largely respiratory-related disease, similar to the ordinal outcome in the ACTT-1 trial. The pulmonary+ outcome has the same categories for pulmonary complications (e.g., requirements for oxygen), and additionally includes extra-pulmonary outcomes such as thrombotic, myocardial, and cerebral complications of COVID-19.

Guidelines for the early futility assessment are as follows:

- a. If the investigational agent is superior to placebo (i.e.,  $p \leq 0.3$  for a one-sided test) in both the pulmonary+ and pulmonary intermediate ordinal outcomes, then enrolment for the agent will expand to complete the trial.
- b. If there is insufficient evidence for superiority versus control (i.e., one-sided  $p > 0.3$ ) in each of the two outcomes, then stop randomization.
- c. If there is evidence (1-sided  $p < 0.3$ ) for an association for one endpoint and not the other, then the agent may or may not advance depending on the risk/benefit profile emerging from the data at this early stage. If the effect estimate for both outcomes is on the side of benefit, the preference would be towards advancing the agent and expanding enrollment to include disease severity stratum 2.

The DSMB will be asked to review whether the discordance is attributable to a positive or negative effect on extra-pulmonary organ dysfunction (the difference in the two ordinal scale categories, the conditions included in pulmonary+ but not in the pulmonary endpoint), and whether the same ordinal outcomes assessed on other days yield similar results, and weigh the risk/benefit profile. For example, if there is a significant positive effect on the pulmonary score and the lack of significant effect on the pulmonary+ score is driven by a lack of difference in the milder thrombotic symptoms in category 4 of the pulmonary+ scale (e.g. deep venous thrombosis) and there is no evidence of any raised risk of thrombosis overall, the agent will advance. Conversely, if the agent is superior to the control group with respect to the pulmonary outcome, but clearly inferior to the control group with respect to the pulmonary+ outcome or has a concerning safety profile, it will not advance.

Analyses of the primary efficacy endpoint, time to sustained recovery, will also be provided to the DSMB, as supporting information. These analyses are described in section [8.1](#).

If available, subgroup analyses by nAb status at study entry (nAb negative or positive) will also be provided.

### 10.2.2 Analyses of the Pulmonary and Pulmonary+ outcomes on Day 5

- Treatment groups will be compared by intention to treat.
- For each of the two ordinal outcomes, the number and percentage of participants in each of the categories on Day 5 will be tabulated, and the OR of the active versus control group will be estimated using a proportional odds model with indicators for the investigational agent group (active versus control) and for the categories of the ordinal pulmonary+ outcome at baseline (to adjust for baseline severity of illness). The model will be stratified by site pharmacy.

The summary tables will show the adjusted summary OR with 95% CI, estimated as described above, as primary analysis. In addition, the unadjusted summary OR with 95% CI will be shown as sensitivity analysis (estimated using a proportional odds model without adjustment for the pulmonary+ baseline category or site pharmacy). In the case that the adjusted OR differs substantially from the unadjusted OR, the reason for the deviation will be explored.

#### Comments:

- Results will be presented such that OR>1 favors the investigational agent, denoting higher odds of more favorable disease categories in the group randomized to investigational agent compared with control.
- In order to avoid overestimating the proportion of participants who died, participants who died prior to Day 5 will only be included in the Day 5 summaries of the pulmonary and pulmonary+ outcomes if their time from randomization to cut-date is at least 5 days, and similarly for analyses on other days. Mortality is a key secondary endpoint and will be summarized cumulatively as an additional analysis.
- **For the initial futility analysis**, the tests comparing the investigational agent versus placebo will be performed using a (1-sided) type 1 error rate of 30%. This means, the investigational agent will be considered “superior” to the control with respect to the pulmonary (or pulmonary+) outcome, if the estimated summary OR is greater than 1, and the p-value  $\leq 0.30$ .

The summary reports will show the estimated summary OR with 95% CI, the signed Z-value for the test statistic comparing the treatment groups, and the one-sided p-value for superiority, calculated in the primary analysis (i.e., using the proportional odds model that is adjusted for the pulmonary+ category at baseline and stratified by site pharmacy, as described above). As sensitivity analysis, these values will also be calculated using the unadjusted proportional odds model and included in the summary report.

**Comment:** At the recommendation of the FDA, for monoclonal antibodies studied, patients requiring high-flow oxygen or mechanical ventilation (invasive or non-invasive) are not eligible for enrolment unless the investigational agent passes the initial futility assessment. At that time, the FDA will be consulted. This was done for AZD7442 after it passed the initial futility

assessment and the FDA allowed expansion of enrollment. This initial enrollment restriction does not apply to investigational agents other than monoclonal antibodies.

If eligibility is restricted to disease severity stratum 1, adjusting the treatment comparison for the pulmonary+ outcome at baseline is identical to adjusting for the following categories defined by oxygen requirement:

- No supplemental oxygen (pulmonary+ category 2)
- Supplemental oxygen  $< 4$  L/min (or  $< 4$  L/min above premorbid requirements) (pulmonary+ category 3)
- Supplemental oxygen  $\geq 4$  L/min (or  $\geq 4$  L/min above premorbid requirements, but not high-flow oxygen) (pulmonary+ category 4)

- To supplement the overall summary odds ratios for the 7-category outcomes, each dichotomized definition of improvement that can be formulated from the components of the ordinal outcomes will be considered separately; for example, treatment groups will be compared for the proportions of participants in category 1 on Day 5, proportions in categories 1 or 2 (“best two categories”), in categories 1-3, etc. Proportions will be tabulated, and odds ratios for active versus control groups will be estimated with 2-sided 95% CIs using logistic regression models. These analyses need to be interpreted with caution, because they are not adjusted for inflation of type I error due to multiple comparisons.
- Subgroup analyses will be carried out for the Pulmonary and Pulmonary+ outcomes on Day 5, to supplement the early futility analyses. The goal is to determine whether the treatment effect differs across subgroups, and to aid the DSMB in considerations on whether there are safety concerns in specific subgroups. Principles for subgroup analyses are described in section 9.1; here, subgroup analyses are based on the proportional odds models. In particular, heterogeneity of the treatment effect across the baseline pulmonary+ categories will be assessed.
- After an investigational agent has passed initial futility assessment and enrollment has been expanded to include participants in disease severity stratum 2, treatment comparisons for the pulmonary and pulmonary+ outcomes on Day 5 continue, and will be performed separately for each of the two disease severity strata, to assess safety for the more severely ill participants in stratum 2.

### **Missing data: Unknown outcome status for the pulmonary or pulmonary+ outcomes on Day 5:**

The following items describe how missing data will be treated for the primary analyses of the pulmonary or pulmonary+ outcomes on Day 5. As needed, these methods may be also applied to analyses at other time points (e.g., Day 7).

- **Interim analyses:**
  - Only participants with Day 5 data for the pulmonary outcome will be included for the Day 5 comparisons. The number and proportion of participants with unknown outcome status will be summarized.

**Comment:** If the cut date is less than 10 days before the data freeze date, Day 5 data for the ordinal outcomes are considered “missing” only for participants with at least 10 days of administrative follow-up.

- **Final analyses** after completion of the trial:
  - If Day 5 data are missing for a substantial proportion of participants (e.g., more than 5% of the mITT cohort), multiple imputation will be used to impute missing Day 5 data for the pulmonary and pulmonary+ outcomes. For the imputation, the following baseline covariates will be considered in addition to the indicator for treatment group: age, sex, country, duration of symptoms prior to enrollment, status of the ordinal pulmonary (or pulmonary+) outcome, and presence of comorbidities. Ten rounds of imputation will be used to estimate the summary odds ratio.
  - The number and proportion of participants with missing data will be reported.

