## Sensitivity analyses

- As sensitivity analyses, the treatment groups will be compared by **modified intention-to-treat (mITT)** after excluding participants who did not receive any of the assigned investigational agent (active or control). This mITT analysis will be provided at important decision points, e.g., when the test statistic approaches the monitoring boundary, and for the final analyses after completion of the trial.
- Treatment groups will be compared for the pulmonary and pulmonary+ outcomes on Days 1-7, to monitor the consistency of the treatment effect over time.

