## 11 Data Completeness and Study Conduct

According to the protocol, the pulmonary and pulmonary+ outcomes will be assessed on days 0-7; the decision rules for the initial futility assessment are based on these outcomes on Day 5. The pulmonary outcome will also be assessed on Days 14 and 28. The primary outcome, "time to sustained recovery", will be assessed through Day 90. Clinical data will be collected on Days 0-7, 14, 28, 60 and 90; mortality and re-hospitalizations will be assessed through 18 months. After hospital discharge, in-person visits are scheduled on Days 1, 3, 5, 28, and 90, when blood is collected (plasma and serum); other visits may be conducted by phone (Days 7, 14, 42, 60, and 75). The data collection schedule is included in [Appendix D](#) of this SAP.

Data completeness and study conduct reports will be provided by treatment group (for the closed report) and pooled across treatment groups (for the open report). Data summaries for the infusion of the investigational agent on Day 0 are described in [Section 6](#); several of those reports are also relevant for monitoring study conduct and will be included in the open report or provided to study leadership, pooled across treatment groups.

The following data summaries will be provided to assess data completeness and study conduct:

- Number and percent of participants with protocol deviations, and type of protocol deviation
- Expected and observed number (% of expected) of participants who completed visits on Days 1-7, 14, 28, 42, 60, 75, and 90.
- Expected and observed number (% of expected) of participants with known outcome status for the pulmonary and the pulmonary+ outcomes on Day 5.
- Ascertainment of the primary outcome: Expected and observed number (% of expected) of participants with known status of "time to sustained recovery" at days 28, 60, and 90. To ascertain "sustained recovery", several elements are required: vital status; the status of hospitalization; if discharged, the status of the residence ("home" versus other).
- Expected and observed number (% of expected) of participants with known vital status at days 5, 14, 28, 60 and 90, and at months 6, 12, and 18.

- Number and percent of participants who withdrew consent or were lost to follow-up (no contact and unknown vital status for 45+ days).

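### The final-analysis imputation of Day 5 pulmonary and pulmonary+ status uses only arm and baseline data, giving up a modest but free gain from the same scales' daily readings

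*SAP*

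**What the plan says.** The rule is in the SAP, section 10.2.2, under the item on unknown Day 5 status.

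- **Final analyses.** Imputation is conditional: "If Day 5 data are missing for a substantial proportion of participants (e.g., more than 5% of the mITT cohort"). The predictors are introduced with "For the imputation, the following baseline covariates will be considered in addition to the indicator for treatment group" and listed as "age, sex, country, duration of symptoms prior to enrollment, status of the ordinal pulmonary (or pulmonary+) outcome, and presence of comorbidities". Because the list is headed as baseline covariates, the ordinal status in it is the Day 0 status. "Ten rounds of imputation will be used to estimate the summary odds ratio".
- **Interim analyses, including the early futility assessment.** There is no imputation: "Only participants with Day 5 data for the pulmonary outcome will be included for the Day 5 comparisons".
- **What is collected.** SAP section 11 states that "the pulmonary and pulmonary+ outcomes will be assessed on days 0-7", and the schedule in Appendix D agrees.
- **What is analysed.** Section 8.3 plans comparisons on Days 1-7. The sensitivity analyses in section 10.2.2 repeat this: "Treatment groups will be compared for the pulmonary and pulmonary+ outcomes on Days 1-7, to monitor the consistency of the treatment effect over time".

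Neither document adds a post-baseline predictor to the imputation model elsewhere.

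**The concern.** A participant who lacks only the Day 5 reading will often have readings on Days 4 and 6. On a seven-category scale driven by oxygen need, those say far more about Day 5 than age, country or Day 0 status. Leaving them out has three possible consequences.

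1. **Precision.** Imputation that cannot predict the missing value returns roughly the complete-case answer.
2. **Bias.** The model treats missingness as unrelated to the course since randomization, given arm and baseline. If that fails, and fails differently by arm, the odds ratio shifts.
3. **Coherence.** Category 7 is death. Nothing in the described model stops a draw of death on Day 5 for someone recorded alive on Day 6, or of category 1 for someone on invasive ventilation on Days 4 and 6.

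At stake are the final Day 5 odds ratios. The rule may also be applied at other time points, such as Day 7.

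**Working it through.** **Step 1. The plan's nearest figure.** The documents give no precision or bias figure for the imputation. The nearest is section 1.4: 300 participants, OR 1.60, one-sided 0.30, power 95%. Whitehead's formula is N = 12(z_0.70 + z_0.95)² / [(ln 1.6)²(1 − Σp̄³)], where p̄ are the mean category proportions. With z values 0.524 and 1.645 and ln 1.6 = 0.470, N = 255.6/(1 − Σp̄³). The control distribution is not given here. N = 300 is exact at Σp̄³ = 0.148, and power runs from 0.966 at Σp̄³ = 0 to 0.943 at 0.20. The stated 95% reproduces.

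**Step 2. Complete-case benchmark.** If a fraction f is missing and nothing is recovered, the SE grows by 1/√(1 − f): 1.026, 1.054 and 1.085 at f = 0.05, 0.10 and 0.15.

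**Step 3. Precision by simulation.**
- From the SAP: N = 1,000 allocated 1:1, seven categories, 10 imputations.
- Assumed: death absorbing, daily latent correlation 0.9, true OR about 1.6, missingness related to Day 4 status equally in both arms. There were 150 replicates per row, combined by Rubin's rules.
- Mean SE of the log OR with complete data: 0.1147.

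| Missing | Arm + baseline: SE (ratio) | Plus Days 4 and 6: SE (ratio) | Share of inflation removed |
|---|---|---|---|
| 5% | 0.1178 (1.027) | 0.1155 (1.006) | (2.7 − 0.6)/2.7 = 78% |
| 10% | 0.1205 (1.051) | 0.1164 (1.015) | (5.1 − 1.5)/5.1 = 71% |
| 15% | 0.1255 (1.094) | 0.1175 (1.024) | (9.4 − 2.4)/9.4 = 74% |

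The baseline-only ratios sit on the Step 2 benchmark. Across the large-sample scenarios of Step 4, baseline-only imputation also gave the complete-case OR to within 0.003.

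**Step 4. Bias, same assumptions, N = 1.5 million.**
- *Missingness tied to Day 4 status equally in both arms.* At 15% missing, baseline-only OR was 1.548 against a full-data 1.558 (0.6% low). With latent correlation 0.95, the largest gap was 1.563 against 1.578 (1.0%).
- *Unequal by arm.* Active-arm participants with good Day 4 status (categories 1-2), or with poor status (categories 4-6), are twice as likely to be missing as everyone else. Full-data OR is 1.554. Baseline-only OR is 1.512 (good missing) or 1.574 (poor missing) at 5%, and 1.462 or 1.599 at 10%. On the log scale the largest of these shifts is 0.441 − 0.380 = 0.061, about half the SE of 0.1205 in Step 3.
- *Stress case.* A five-fold imbalance at 10% missing gives about 1.36 or 1.73 against about 1.56. The models with Day 4, or Days 4 and 6, were run here and recovered the full-data OR to within 0.003. Missingness was generated from Day 4, so this recovery is partly built in.

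A simpler linear analogue (N = 1,400, true OR 1.60) agrees in pattern. With missingness driven by early improvement in one arm only, the baseline-only OR is 1.54, 1.50 and 1.44 at 5%, 8% and 12% missing. With the same mechanism in both arms it is 1.59.

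**The case against.** A reader might infer that the rule biases the Day 5 odds ratio as a matter of course, or that it weakens the decision to continue an agent. The documents support neither.

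- **Bias.** A material shift needs missingness that follows clinical course differently by arm. The trial is randomized and blinded, and no passage points to arm-specific missingness. With a common mechanism the error is about 1% or less, and under imbalance its direction depends on who is missing. This objection stands.
- **Reach.** The futility assessment uses observed Day 5 data only, and the primary endpoint is time to sustained recovery. At the final analysis the Day 5 scales are among the other secondary outcomes in section 8.3. This stands.
- **The trigger may not be met.** No Day 5 missingness rate is given. In Table E-1 for AZD7442, recovery status was lost or unknown for 6 + 23 + 4 = 33 of 1,417 infused participants (2.3%). Appendix D provides for a telephone call on the study day when a Day 3 or Day 5 in-person visit is not possible. This makes heavy Day 5 loss less likely, although neither fact measures intermittent Day 5 gaps.
- **Neighbouring days do not always exist.** After withdrawal there is no Day 6 or 7, so only earlier days help. This stands as a limit on the gain.
- **Flexibility.** The covariates are only to be considered, and section 1.1 lets blinded statisticians update the SAP before unblinding. That permits a better model but does not specify one, and choosing predictors after unblinding would be post hoc. This does not answer the point.

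**Conclusion.** The omission is plain in the text, and a better model is available from planned data. Its cost is modest: about 2.7% on the SE of the log OR at the 5% trigger and 5% at 10% missing, reducible to about 0.6% and 1.5%. Beyond precision, the fuller model protects against bias if missingness tracks early course differently by arm, and it avoids imputed values that contradict the record. Claims beyond this, such as a standing bias or a threat to futility decisions or the primary result, are not supported.

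The omission itself is certain. The sizes rest on assumed category distributions, correlations and missingness mechanisms, and on Day 5 missingness rates that the documents do not report. This is a worthwhile, low-priority improvement.

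**What to change.** In section 10.2.2, extend the imputation model for final analyses. Keep treatment arm and the listed baseline covariates, and add the participant's available pulmonary and pulmonary+ categories from Days 1-4, 6 and 7, together with known vital and discharge status. Say that whichever days exist will be used: both sides of an intermittent gap, and only earlier days after withdrawal. Require imputed values to agree with recorded status, so that, for example, death on Day 5 cannot be drawn for a participant known to be alive later. If the method is used at another time point such as Day 7, the neighbouring days should change accordingly.

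The cost is SAP wording and programming, settled before unblinding. The variables are already collected, so there is no change to visits, sample size or the interim rules.
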